6.1 Lead-in Dose Escalation Evaluation

The study will begin with a lead-in phase dose escalation evaluation of two dose levels of each investigational agent in combination with Nivolumab, in cohorts of 3 to 8 CIT-experienced patients each. Table 5 lists the planned dose levels for each agent, with the starting dose for each agent shown as Dose Level 1.

Patients may be escalated to Dose Level 2 or de-escalated to Dose Level -1, depending on safety observations.

Table 5: Investigational Study Drug Starting Dose Levels for Cohorts of Patients in the Lead-In Phase Dose Evaluation

Drug	Regimen	Dose Level		
		1	2	-1
Glesatinib Tablets	Twice Daily	500 mg	750 mg	350 mg
Sitravatinib Capsules	Once Daily	120 mg	150 mg	80 mg
Mocetinostat Capsules	Three Times Weekly	70 mg	90 mg	50 mg

Depending on experience in early cohorts of patients in the lead-in phase dose escalation evaluation, doses below those shown in Table 5 may be implemented in subsequent cohorts of patients after discussion among Investigators participating in the lead-in phase evaluation and the Sponsor. Depending on experience with early cohorts of patients, not all dose levels may be explored.

Throughout the study, Nivolumab will be administered in accordance with approved labeling. Nivolumab is to be administered by intravenous infusion, using either regimen included in the approved label: 240 mg every 2 weeks (Q2W) or 480 every 4 weeks (Q4W). Guidance for adverse event management and associated Nivolumab treatment modifications are provided in the product labeling and replicated in Section 5.2 of the protocol.

6.1.1 Definition of Dose Limiting Toxicity (DLT)

The National Cancer Institute Common Toxicity Criteria for Adverse Events (NCI CTCAE) v4.03 will be used for the evaluation of safety observations throughout this study. The definition of DLT for the purpose of dose escalation decisions includes any of the following events considered to be causally related to treatment with an investigational study drug in combination with Nivolumab that occurs during the first 28-day treatment cycle:

- Any Grade 4 non-hematological toxicity.
- Any Grade 3 non-hematological toxicity or Grade 3 or 4 hematological toxicity that does not recover to ≤ Grade 2 as indicated by symptoms within 3 days and/or as indicated by laboratory assessment within 8 days after onset of the event despite optimal medical management with or without corticosteroids.
 - A special case is provided for hepatic transaminases – increase over baseline by two-fold or more and meeting Grade 3 or 4 criteria.
- Grade 2 pneumonitis or colitis that does not resolve to ≤ Grade 1 as indicated by symptoms within 3 days after onset of the event despite optimal medical management with or without corticosteroids.
- Febrile neutropenia or neutropenia associated with systemic infection.

- Any toxicity that requires suspension of treatment for more than 2 weeks.

The definition of DLT excludes the following conditions:

- Grade 3 fatigue lasting ≤ 7 days.
- Grade 3 endocrine disorder (thyroid, pituitary, and/or adrenal insufficiency) that can be effectively managed with hormone replacement therapy.
- Acute infusion-related reaction.
- Lymphopenia without infection.
- Thrombocytopenia without clinically significant bleeding.

6.1.2 Enrollment and Dose Escalation Plan

Patients meeting eligibility criteria as outlined in the protocol may enroll into the lead-in phase dose escalation evaluation, regardless of whether they did or did not experience clinical benefit during prior treatment with a checkpoint inhibitor.

Dose escalation cohorts are expected to include between 3 and 8 patients for each investigational study treatment and dose level evaluated. The first patient to be treated at the starting dose and at each new higher dose of investigational study drug will be observed for at least 1 week prior to enrollment of subsequent patients in the cohort. As many as 5 patients may initially be enrolled into each cohort. For a patient within a dose cohort to be considered evaluable for the dose-escalation decision, the patient must have either been on study for 1 full cycle and have received treatment with Nivolumab and at least 75% of scheduled investigational study drug doses in Cycle 1 or have experienced a DLT in Cycle 1.

Decision making for cohort expansion and dose escalation or de-escalation will be in accordance with the modified toxicity probability interval (mTPI) method (Dose-Finding Spreadsheet presented in Appendix 2 of the protocol). To ensure sufficient patient experience at the dose to be used in the Phase 2 study, enrollment at any dose level under consideration may be expanded to include at least 6 patients.

6.1.3 Definition of Maximum Tolerated Dose (MTD)

The Maximum Tolerated Dose (MTD) for each combination regimen is defined as the highest investigational study drug dose administered in the combination regimen associated with the decision to “stay with the current dose” as determined from the Dose-Finding Spreadsheet (Appendix 2 of the protocol) using the experience of at least 6 patients during the first 28-day treatment cycle.

6.1.4 Selection of Phase 2 Dose for Investigational Study Drugs

For each investigational study drug, the dose to be selected for use in the Phase 2 study will be the highest dose evaluated in the lead-in phase evaluation that is associated with:

- sufficient safety/tolerability to anticipate that patients will typically be able to receive treatment with at least 75% of the intended dose intensity of investigational study drug and 100% dose intensity of Nivolumab; and
- no observed ≥Grade 3 or serious immune-related adverse events (irAEs) causally related to the combination regimen.

A dose level below the MTD may be selected for use in the Phase 2 study.

6.2 Phase 2 Study

Following completion of the lead-in phase dose escalation evaluation, enrollment into the Phase 2 study will proceed. The treatment arms included in this study are the following:

1. Glesatinib plus Nivolumab
2. Sitravatinib plus Nivolumab
3. Mocetinostat plus Nivolumab

For patients who have experienced progression of disease on or after treatment with a checkpoint inhibitor (CIT-experienced) enrollment into each treatment arm will be stratified by prior outcome of treatment with a checkpoint inhibitor:

- a. Clinical benefit (i.e., RECIST defined CR, PR or SD for at least 12 weeks [-2 week window permitted for radiograph scheduling]) followed by radiographic progression of disease.
- b. No prior clinical benefit (i.e., radiographic progression of disease \leq 12 weeks after initiation of treatment [+2 week window permitted for radiograph scheduling]).

Thus, the study will include 6 parallel evaluations of clinical activity of Nivolumab combination regimens (Figure 1) in patients with prior treatment with a checkpoint inhibitor. Patients enrolled in the lead-in phase dose escalation evaluation and receiving the dose of investigational study drug chosen for the Phase 2 study will be included in the analysis of the Phase 2 endpoints. Patients who discontinue the study prior to the first on-study disease assessment for reasons other than disease progression may be replaced.

For patients without prior CIT (CIT-naïve), each investigational study treatment arm (i.e., Glesatinib and Sitravatinib) will be stratified according to PD-L1 status:

- a. Having tumor with no/low PD-L1 expression.
- b. Having tumor with high PD-L1 expression.

Tumor PD-L1 expression will be determined by the PD-L1 (28-8) companion diagnostics assay completed through the central laboratory. No/low PD-L1 expression is defined as positivity $< 5\%$ of tumor cells; high PD-L1 expression is defined as positivity $\geq 5\%$ of tumor cells. Tumor samples used to establish PD-L1 expression for eligibility must have been collected after the most recent systemic therapy.

Thus, the study will include 6 parallel evaluations of clinical activity of Nivolumab combination regimens (Figure 1) in patients without prior treatment with a checkpoint inhibitor.

Disease response and progression as documented by the Investigator in the CRF will be the basis for patient management and study expansion decision making. Unconfirmed objective responses recorded in the CRF may be used as the initial basis for expansion of study enrollment; however, follow-up evaluations on patients with unconfirmed responses must continue to support the decision to continue to the full number of patients to be included in the next stage. Disease assessments will be performed until objective disease progression is documented or subsequent anti-cancer therapy is begun. Central radiology review for disease response and progression may be added to the study during Stage 2. If this occurs, central review of all radiologic assessments performed in the study will be conducted (including retrospective review of patients enrolled in Stage 1), and central radiology review for disease response will be the basis for the primary statistical analyses to estimate the objective response rate and its confidence interval (CI), as well as the DoR and PFS.

6.2.1 Sample Size Considerations

Approximately 24 patients may be enrolled into the lead-in phase of the study. A precise sample size cannot be defined as it is dependent on the number of dose escalations based on the mTPI (Ji 2013) method, and the number of patients enrolled in the expansion cohorts

6.2.1.1 Lead-In Phase

The mTPI method will be employed in decision making concerning dose escalation within each regimen investigated. The assumptions to be applied in establishing the mTPI methodology are:

- Each specific regimen exploration will include up to 30 patients
- The MTD is defined to have 0.25 probability of toxicity; and
- The acceptable variance around the MTD is ± 0.05 (i.e., the region of the MTD is 20% to 30% incidence of DLT).

6.2.1.2 Phase 2 CIT-experienced and CIT-naïve with no/low PD-L1 expression

This Phase 2 study will use a Predictive Probability Design (Lee 2008) in each treatment arm and strata. In creating the statistical designs, the Type 1 error (α) is constrained to <0.05 and power ($1-\beta$) is constrained to ≥ 0.90 .

The ORR using Nivolumab in the population with advanced non-squamous NSCLC having prior disease progression on a checkpoint inhibitor or patients with non-squamous NSCLC without prior CIT with no/low PD-L1 expression is assumed to be 5% (p_0); thus this rate is considered uninteresting. The target ORR using the investigational agents in combination with Nivolumab in this study is 30% (p_1). Stage 1 of enrollment will include a minimum of 9 evaluable patients in each treatment strata. With exactly 9 evaluable patients at Stage 1, if at least 1 patient has an Objective Response, 8 additional evaluable patients will be enrolled in the treatment stratum, for a total sample size of 17 evaluable patients. If at least 3 Objective Responses are observed in a treatment stratum, further investigation may be warranted. If the true ORR is 5% (null hypothesis), the probability of early termination during the study is 0.63; the Type 1 error is equal to 0.0466 and the power is equal to 0.9045.

6.2.1.3 Phase 2 CIT-naïve with high PD-L1 expression

The ORR using Nivolumab in the population with non-squamous NSCLC having high PD-L1 expression is assumed to be 27% (p_0); thus this rate is considered uninteresting. The target ORR using the investigational agents in combination with Nivolumab is 50% (p_1).

Stage 1 of enrollment will include approximately 17 evaluable patients. With exactly 17 evaluable patients at Stage 1, if at least 5 patients have Objective Responses, 27 additional evaluable patients will be enrolled, for a total sample size of 44 evaluable patients. If at least 18 Objective Responses are observed, further investigation may be warranted. If the true ORR is 27% (null hypothesis), the probability of early termination during the study is 0.50; the Type 1 error is equal to 0.0303 and the power is equal to 0.9018.

The exact stopping rules for all cohorts will be calculated based on the Predictive Probability Design, once the exact number of patients evaluable at Stage 1 is known. The aim is to get a minimum of 9 evaluable patients at Stage 1 for CIT-experienced and CIT-naïve with no/low PD-L1 expression cohorts and a minimum of 17 evaluable patients at Stage 1 for CIT-naïve with high PD-L1 expression cohort.

The original protocol provided that if results in any strata were of high interest for efficacy, enrollment might be expanded to as many as 100 patients total in each cohort to narrow the 95% CI around the ORR point estimate. Protocol Amendment 3 (v4.0) eliminates enrollment expansion beyond Stage 2 except in the Sitravatinib segment of the study enrolling patients with CIT-experience.

6.2.1.4 Expansion Beyond Phase 2

For the Sitravatinib segment of the study enrolling patients with CIT-experience, expansion of enrollment beyond Stage 2 will be managed as one cohort that includes all patients, regardless of prior clinical benefit during treatment with CIT. Based on preliminary clinical activity results as of June 2018 (described in Section 1.5.3.2.2 of the protocol), enrollment into the combined cohort will expand to as many as 125 patients total, to further evaluate safety and efficacy in this setting.

[figure not shown]
Expansion of Sitravatinib CIT-naïve cohorts beyond Stage 2 of enrollment is not anticipated.

6.3 Randomization

Random assignment to treatment arms is not being used in this study. Treatment arm assignment will be determined by the site where the patient is enrolled as described in Section 6.0.

Figure 1: Phase 2 Portion Study Diagram

7.0 Analysis Populations

Patients who consent to be part of the PK sub-studies will be excluded from all populations, with the exception of the enrolled population and the PK sub-study population.

7.1 Enrolled Population

The Enrolled Population is defined as all patients who sign an informed consent and are determined by the Investigator to meet all eligibility criteria during screening assessments. Percentages in the disposition summaries will be displayed using the Enrolled Population as the denominator.

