4.1.5 Sitravatinib Pharmacokinetic Sub-Studies

Two Sitravatinib sub-studies were added to protocol v4.0, however as per the project administrative letter, dated July 15th 2020;

- PK Formulations of capsules (Appendix 5 of protocol v6):

This was intended to be an evaluation of Sitravatinib PK using three formulations of capsules. The objective of this sub-study was fulfilled in a healthy volunteer study (516-006) which demonstrated bioequivalence between the 100 mg Sitravatinib malate capsule formulation (test) and the 120 mg Sitravatinib free base capsule formulation (reference). Therefore, no additional data are needed.

- PK Food sub-study (Appendix 6 of protocol v6):

This was intended to be an evaluation of PK when Sitravatinib capsules are administered orally in the fed state. Mirati Therapeutics has decided to conduct a separate study to evaluate the pharmacokinetics of Sitravatinib with and without food. Therefore, the Pharmacokinetic Food Effect Sub-Study (Appendix 6) will be closed.

As a result, the PK sub-study component of this study will be comprised of selected Demographic and Safety summaries, as described in Section 11.2. Patients from these PK sub-studies will be excluded from the main study summaries, their data will be listed separately.

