7.6 PK Sub-Study Population

The PK sub-study population is defined as any patient consenting to be part of either the PK formulation or the PK food effect sub-studies. Consent will be identified programmatically from the Study Treatment Assignment page of the CRF.

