11.0 Planned Analysis

PK sub-study patients will be excluded from any main study summaries and will be presented in PK sub-study specific summaries only. Screen Failures will be summarized in a Screen Failure table, but otherwise excluded from all tables and listings. Listings will include all relevant derived variables.

All data collected during this study will be displayed in data listings, unless otherwise specified. Data listings will be presented separately for enrolled patients in the main study and those in the PK sub-studies.

Descriptive statistics (mean, median, standard deviations [STD] or standard error, first quartile [Q1], third quartile [Q3], minimum and maximum values) for continuous variables will be presented. Mean and median will be presented to 1 decimal more than original data. STD will be presented to 2 decimals more than original data. Minimum and maximum values will match the decimal points in the original data. For categorical variables, summary measures will include the frequency and percentage (with 1 decimal place) of patients in each category.

Safety summaries will be presented for assessments on-treatment (as defined in Section 8.4) and will include patients from both the safety lead-in and phase 2 parts of the study. Efficacy summaries will be presented for assessments on-study (defined in Section 8.2) and will include patients receiving the recommended phase 2 dose (120mg QD) only. All tables will be presented by treatment arm and strata.

Unless otherwise noted, missing data will not be imputed or carried forward.

All data summaries and tabulations will be prepared with SAS® v9.4 or higher.

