11.1 Analysis for Main Study (non PK sub-studies)

11.1.1 Patient Disposition

The number and percentage of patients in each analysis population will be presented, along with the patients who withdrew from the study, discontinued Nivolumab or the investigational study drug, with the breakdown of corresponding withdrawal/discontinuation reasons. The number and percentage of deaths, including cause of death and the duration on treatment (time from first dose date to end of treatment, in months) will also be presented.

The number of patients enrolled by site and overall will be presented.

Disposition will be summarized descriptively by treatment arm and strata.

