11.2 Analysis for PK Sub-Studies

The two sub studies described in Appendix 5 and Appendix 6 (Food Effect Study) of the protocol were closed early, refer to Section 4.1.5 for details on this change from the protocol. The sub-study component of the CSR will now consist of only selected demographic and safety summaries, with a standalone PK analysis plan covering the details of any analysis and reporting of PK parameters and related concentration summaries.

All PK sub-study summaries falling within the scope of this SAP will be based on the PK sub-study population. Each summary table will be presented by strata and then by cohort, with 3 cohorts for the formulation study (one for each formulation type), one cohort for the food effect study (fed state) and an overall total across all 4 cohorts presented side by side.

The following selected analysis will be presented separately for each sub-study (formulation and food effect):

- Demographic Characteristics
- TEAEs by SOC and PT
- Treatment Related TEAEs by SOC and PT
- TEAEs by SOC, PT and Maximum CTCAE Grade
- Treatment Emergent SAEs by SOC and PT

All main study safety listings will be repeated for the PK sub-study patients.

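### The PK sub-study adverse-event tables divide by consenting rather than dosed patients, and the main-study disposition denominator needs one clarifying line

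*SAP*

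**What the plan says.** **Sub-study safety tables.** SAP 7.6 sets the population: "The PK sub-study population is defined as any patient consenting to be part of either the PK formulation or the PK food effect sub-studies". It adds that consent is read from the CRF page recording treatment assignment, and it sets no dosing condition. SAP 11.2 then states: "All PK sub-study summaries falling within the scope of this SAP will be based on the PK sub-study population". The tables it lists include TEAEs (all, treatment-related, and by maximum grade) and treatment-emergent SAEs.

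SAP 7.4 and protocol 9.3.3 define the safety set as patients given either drug at least once, and both assign that set to every safety analysis. SAP 7.0, however, says that PK sub-study patients "will be excluded from all populations, with the exception of the enrolled population and the PK sub-study population", so they are outside the Safety Population.

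**Main-study disposition.** SAP 7.1 states: "Percentages in the disposition summaries will be displayed using the Enrolled Population as the denominator". Under 7.0, sub-study patients belong to that population. SAP 11.0 states: "PK sub-study patients will be excluded from any main study summaries and will be presented in PK sub-study specific summaries only", and 4.1.5 agrees: "Patients from these PK sub-studies will be excluded from the main study summaries, their data will be listed separately". The disposition table itself is described in 11.1.1, which sits under the main-study heading: "The number and percentage of patients in each analysis population will be presented".

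**The concern.** An incidence table needs a denominator of patients who could have had the event. For TEAEs that means dosed patients. The sub-study tables use consenting patients instead, and SAP 7.0 leaves no dosed set for them to fall back on. SAP 4.1.3, which lists the changes to analysis populations, does not mention this departure from protocol 9.3.3. Because the cohorts are small, one undosed patient would visibly shift an incidence figure in a table meant to describe the safety of each formulation or of dosing with food.

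The disposition point is one of consistency. Two sets of sections give different answers on whether sub-study patients are in the main-study denominator. Under one answer, each of them would look like someone who enrolled and never reached the FAS or Safety Population.

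**Working it through.** The plan states no figure on either point, so there is none to reproduce.

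**A. Sub-study safety tables**

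The sections, in order:
- 8.4.1.1: a TEAE starts or worsens after first dose, so an undosed patient can never be in the numerator.
- 7.6 with 11.2: an undosed patient who was assigned to a sub-study is in the denominator.
- 7.0: no sub-study patient is in the Safety Population, so 7.4 does not correct this.

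Let n be the patients in a cohort and u the number never dosed. Then reported incidence = incidence among dosed × (n − u)/n.

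Inputs: n is at most 12 per formulation cohort (protocol Appendix 5) and at most 10 per food-effect cohort (Appendix 6). The documents do not give u, so the values below are assumptions.

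- n = 12, u = 1, three patients with the event: 3/11 = 27.3% among dosed patients, and 3/12 = 25.0% as the SAP would print it.
- For a rate of 50% among dosed patients:

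| | u = 0 | u = 1 | u = 2 |
|---|---|---|---|
| n = 12 | 50.0% | 45.8% | 41.7% |
| n = 10 | 50.0% | 45.0% | 40.0% |

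With u = 0 there is no effect.

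**B. Main-study disposition**

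Let M be the main-study enrolled patients and K the sub-study patients left in the same column's denominator. Then reported % = true % × M/(M + K).

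Which sub-study patients share a column with the main study? SAP 11.1.1 presents disposition by treatment arm and stratum, and SAP 4.2.2 makes dose level part of the arm. Appendix 5 doses its cohorts at 120 mg (free base), 60 mg and 100 mg (both malate). Only the first matches the main-study 120 mg arm, which gives K of at most 12. If the food cohort also received 120 mg (an assumption), K is at most 12 + 10 = 22.

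M = 125 is also an assumption. It is the ceiling for the combined CIT-experienced sitravatinib cohort (SAP 6.2.1.4), not an observed count.

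- K = 12: 125/137 = 0.912, so a true 60% prints as 54.7%.
- K = 22: 125/147 = 0.850, so a true 60% prints as 51.0%.
- If M were 200 instead: 200/212 = 0.943 and 200/222 = 0.901.
- If 11.0 governs, K = 0 and the factor is 1.00.

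**The case against.** **On the safety tables.** The set is identified from the treatment-assignment page rather than from consent forms alone, and SAP 11.0 removes screen failures from all tables but their own. Only a patient who was assigned and then never dosed would matter, and nothing in the documents shows that there was one. The sub-studies were closed early, their tables are descriptive, no test or decision rests on them, and 11.2 repeats the safety listings for these patients. All of this stands, and it limits the size. It does not supply a dosed denominator, and no other section does.

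**On disposition.** A patient excluded from a summary is ordinarily outside both its numerator and its denominator. SAP 4.1.5 and 11.0 say these patients are excluded, and 11.1.1 is placed under the main-study heading. This is the more natural reading and it largely answers the point. What remains is that, on this reading, keeping these patients in the Enrolled Population changes no disposition percentage. SAP 11.2 plans no sub-study disposition table in which that membership could be used. A programmer working from 7.0 and 7.1 alone could reasonably leave them in.

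**A stronger reading.** A reader might infer that the reported percentages are too low, or that every disposition percentage shrinks by one pooled factor. The documents support neither. The safety effect needs an undosed patient, and the disposition effect needs 7.0 and 7.1 to override 11.0. A pooled factor cannot apply across columns split by arm and dose: the 60 mg and 100 mg cohorts fall outside the 120 mg arm, and the glesatinib arm has no sub-study patients at all.

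**Conclusion.** The safety point holds as a defect of definition. SAP 7.6 and 11.2 pair a numerator restricted to dosed patients with a consent-based denominator, contrary to protocol 9.3.3 and to SAP 7.4. Its effect is zero if every assigned patient was dosed. Otherwise one undosed patient in a cohort of 12 lowers any incidence by a factor of 11/12, as in 27% becoming 25%.

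The disposition point is an inconsistency to reconcile, not a demonstrated bias. Under the literal reading of 7.0 and 7.1, the factor in the 120 mg arm would be 0.91 to 0.85, given the assumed 125 main-study patients and ceilings of 12 to 22 sub-study patients. Under 11.0 there is no dilution.

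ORR, the secondary efficacy endpoints and the main-study safety percentages are unaffected, because these patients are outside the FAS, CAE and Safety Populations.

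**What to change.** 1. In SAP 7.6 and 11.2, define a sub-study safety set of sub-study patients dosed at least once with sitravatinib or nivolumab, and use it for every sub-study TEAE and SAE table. Keep the consent-based set for listings.
2. In SAP 7.1 or 11.1.1, state that the denominator for main-study disposition is enrolled patients who are not in a PK sub-study. If sub-study disposition is to be summarized, give it its own table and denominator.
3. Record the sub-study safety set in SAP 4.1.3, so that the treatment of these patients relative to protocol 9.3.3 is visible.

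The cost is two definitions, a line in 4.1.3 and one population flag in programming. No new data are needed.
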